6.3 Reporting Procedure

6.3.1 AEs and SAEs

All adverse events and serious adverse events will be recorded in the patient's CRF. A SAE in a patient without HAI must also be reported from the investigator to the Sponsor, within the proper timelines.

SAEs must be reported to sponsor within 24 hours after the site has gained knowledge of the SAE. Every SAE must be documented by the investigator on the SAE pages to be found in as part of the CRF. The Serious Adverse Event Report Form must be completed, signed. The initial report shall promptly be followed by detailed, written reports if necessary. The initial and follow-up reports shall identify the trial subjects by unique code numbers assigned to the latter.

The sponsor keeps detailed records of all SAEs reported by the investigators and performs an evaluation with respect to causality and expectedness. Based on, among other, SAE reports the sponsor will evaluate whether the risk/benefit ratio associated with study is changed.

6.3.2 SUSARs

SUSARs will be reported to the Competent Authority according to national regulation. If both the investigator and the Sponsor find the event to be related to a non-IMP, this SAR does not need to be reported as a SUSAR. However, new side-effects of approved drugs should be reported to National Competent Authorities in accordance with normal clinical practice.

The following timelines should be followed:

The sponsor will ensure that all relevant information about suspected serious unexpected adverse reactions that are fatal or life-threatening is recorded and reported as soon as possible to the Competent Authority in any case no later than seven (7) days after knowledge by the sponsor of such a case, and that relevant follow-up information is subsequently communicated within an additional eight (8) days.

All other suspected serious unexpected adverse reactions will be reported to the Competent Authority concerned as soon as possible but within a maximum of fifteen (15) days of first knowledge by the sponsor.

6.3.3 Annual Safety Report

Once a year throughout the clinical trial, the sponsor will provide the Competent Authority with an annual safety report. The format will comply with national requirements.

6.3.4 Clinical Study Report

The adverse events and serious adverse events occurring during the study will be discussed in the safety evaluation part of the Clinical Study Report.

6.4 Procedures in Case of Emergency

Administration of study treatment will be performed in a setting with emergency medical facilities and staff who are trained to monitor for and respond to medical emergencies. Medical emergencies during the study will be handled according to standard operating procedure at Department of Transplantation Medicine/ Department of HBP surgery at Rikshospitalet

All adverse events and serious adverse events will be recorded during the trial until resolved.

6.5 Data Monitoring Committee (DMC)

In case of death occurs in the HIA/FUDR arm, the independent Data Monitoring Committee (DMC) will recommend whether to continue, modify or terminate the trial.

The DMC will consist of two independent liver surgeons, [name] and [name] who both are employed at hospitals outside of Oslo University Hospital.

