5.1.4.5 Pump removal

In the case of progressive disease or any other reason where use of pump/catheter in HAI group becomes obsolete and is not acceptable to the patient, the pump may be removed (at OUH, dept of GI surgery, HPB-section) through a local incision. The catheter will be ligated and left in situ. In the case of liver resection the catheter may be removed (with the pump) or left in situ, at the surgeon's discretion. During longer drug-free periods, a glycerol solution will be added in the pump chamber to prevent thrombosis of the catheter until the next treatment cycle. Post-resectional use of HAI will be off protocol.

5.1.4.6 Dosage of FUDR, Dexamethasone (Dex), proton pump inhibitors and pump administration.

All patients start HAIP chemotherapy 4 to 8 weeks after surgery, after confirmation of bilobar hepatic perfusion and lack of extrahepatic perfusion.

The pump reservoir is filled percutaneously with 0.12 mg/kg floxuridine together with 35,000U of heparin, 25 mg of dexamethasone and enough normal saline for a total volume of 35cc. Both are to be delivered as a 14-day continuous infusion through the pump. For patients who are more than 25% above ideal body weight, the actual dose of floxuridine is calculated by using a weight that averages the patient's actual weight and their ideal weight.

Patients will commence treatment at a minimum 2 weeks after pump placement. Therapy will be administered in a 4-week cycle. HAI therapy starts on day 1 of each cycle, and the pump will be emptied and filled with heparin (35,000 units) and normal saline on day 15. Systemic chemotherapy will be administered on day 2 and day 16 of each cycle.

Until completion of HAI chemotherapy, patients will receive prophylactic proton pump inhibitor 20mg once daily.

To assess early side effects and toxic reactions, patients will be hospitalized at the Gastrointestinal ward at Rikshospitalet for 24 hours following start of first FUDR administration. At later occasions, the treatment will be offered as an outpatient procedure.

5.1.4.7 Drug Information floxuridine.

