The drug that is used for HAIP is fluorodeoxyuridine or floxuridine (FUDR, Fresenius Kabi, LLC, USA). Floxuridine has been administered using HAI pumps since the early 80s for patients with CLM in the adjuvant, neo-adjuvant, and induction chemotherapy setting. Floxuridine has a half-life of 10 minutes and the liver extracts 95% of floxuridine during the first pass. Toxic effects have been well characterized and are described in detail below. The most important serious adverse drug reaction is biliary toxicity.

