5.1.4.8 Dose adjustments

Patients' complete blood counts and liver function tests are monitored every 2 weeks during HAIP chemotherapy. In the case of abnormal blood tests, dose reduction or postponement of HAIP chemotherapy is done according to the protocol (Table 2) that has been used at MSKCC for many years.

Table 2 complete blood counts and liver function tests:

	Reference Value (RV)*	% Floxuridine dose
Aspartate aminotransferase	2-3 * RV	80%
	3-4 * RV	50%
	>4 * RV	Hold
Alkaline phosphatase	1.2-1.5 * RV	50%
	>1.5 * RV	Hold
Total bilirubin	1.2-1.5 * RV	50%
	>1.5 * RV	Hold

**Reference value is defined as the patient's value on the first day of the most recent floxuridine dose.*

If treatment is held for any of the above situations, treatment will not be reinstated until values come down below 3* RV for aspartate aminotransferase or below 1.2*RV for alkaline phosphatase or total bilirubin, at which time treatment will resume at 25% of the last dose received.

If the patient develops a total bilirubin level above 51mmol/L (i.e. 3.0 mg/dL), the pump should be emptied and dexamethasone 25mg plus 35,000 U of heparin and enough normal saline to fill the pump reservoir should be placed in the pump for 14 days. Once there is no longer evidence of toxicity, the dexamethasone dose should be tapered in increments of 5mg every 14 days. Tapering will continue unless enzymes increase. Floxuridine should be permanently discontinued. Epigastric pain unresponsive to H2 blocker use should prompt a diagnostic workup including a technetium scan to rule out extrahepatic perfusion and an upper endoscopy to assess ulcer disease.

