5.1.4.11 Expected complications related to the HAI pump

Surgical complications related to HAI pump placement may occur. A retrospective review of 544 HAI pump placements was performed at MSKCC.(19) Pump placement was typically combined with a partial liver resection. A simultaneous partial colectomy was performed in 136 patients (25%). No mortality attributed to the pump was reported. The most common complications were unrelated to the pump: wound infection of the laparotomy wound, atelectasis, prolonged ileus, and intra-abdominal abscess. Pump related morbidity (including dysfunction) occurred in 120 patients (22%). HAIP chemotherapy with floxuridine was impossible or discontinued in only 9% of patients. In 9 patients (2%) extrahepatic perfusion was found postoperatively, which could be resolved in 7 patients. In 9 patients (2%) postoperative technetium scan showed incomplete liver perfusion. Most common explanation was a non-ligated accessory or replaced hepatic artery, which was resolved with embolization or surgical ligation. Cross-over flow developed instantly or could be confirmed after four weeks. Hepatic arterial thrombosis can occur immediately after surgery (13 patients, 2%), of which a third could be salvaged with anti-coagulation. Thrombosis also occurred in 11 patients (2%) as a late complication resulting from HAIP chemotherapy. However, in the second half of the study only one patient developed a hepatic arterial thrombosis. The higher incidence in the first half was attributed to the intra-arterial administration of mitomycin C. Pump pocket infection was found in 24 patients (4%) and could be salvaged with parenteral antibiotics in half of these patients. In some patients with pump site infection, replacement and repositioning of the pump may be necessary. Simultaneous partial colectomy did not increase the rate of pump pocket infection. Arterial haemorrhage occurred in only 1 patient. The incidence of biliary sclerosis due to HAIP chemotherapy in a retrospective analysis of 293 patients was 5.5%. Risk factors most significantly associated with biliary sclerosis were dose, number of cycles, abnormal nuclear medicine scan, and postoperative infections. All patients were managed successfully with biliary stenting and/or dilatation.(28)

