 - Monthly pregnancy testing should be performed in women of childbearing potential (WOCBP) as long as they receive chemotherapy according to study protocol. This can be done with a urine test at home combined with contact with the study team by phone
 - A calendar for oncologist visits and provision of systemic chemotherapy is created by coordinating nurse. Control scans are ordered for each 2nd month for the first year following randomization and as long as the patients receive chemotherapy, each 3rd month for the second year and each 6th month for the third year. MDT meetings are scheduled for one week following each new scanning to assess response and possible resectability
 - Out-patient control appointments are scheduled for outcome assessment including QoL-scoring (3, 6, 9, 15, 18, 21 and 24 months)
- Patients in HAI group (group 2 a and 2b)
 - A calendar of reservoir refills is created and harmonized with provision of systemic treatment.
 - A laparotomy is performed within 2 weeks from randomization with insertion of catheter and reservoir for HAI-pump.
- Patients in transplant group
 - Oncologists are instructed to avoid Avastin in systemic chemotherapy while the patient is listed.

Table 3: Overview of screening procedures, End of study/Withdrawal

Overview of screening procedures, End of study Withdrawal												
Item	ICF	Inc/Ex	Med Hist	Prior Trea	Phys Exam	Vit Sign	ECOG	CT/ MR	QoL	Blood Sample	Adverse Event	Survival Assessment
Screening	x	x	x	x	x	x	x	x	x	x	x	
EOS/Withdrawal											x	x

Table 4: Calendar of cycles and events for patients in HAI group

Calendar of cycles and events for patients in HAI group								
Day cycle 1 + 2	1	2	15	16	29	30	44	
Day cycle 3 + 4	61	62	75	76	89	90	104	
Pump refill FUDR at OUS	x				x			
Pump refill HepNaCl at OUS			x					x
Systemic chemo local hospital		x		x		x		

Table 5: Calendar of cycles and events for patients in control group and on waiting list for LTx-group

Calendar of cycles and events for patients in control group and on waiting list for LTx- group							
Day cycle 1 + 2	1		15		29		44
Day cycle 3 + 4	61		75		89		104
Systemic chemo local hospital	x		x		x		x

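### Section 6.5 convenes the DMC only on a death in the HAI arm, so an excess of expected, non-fatal biliary toxicity has no route to the independent committee (narrow gap, low to modest priority)

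*Protocol*

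**What the plan says.** - **The DMC's role.** Section 6.5: "In case of death occurs in the HIA/FUDR arm, the independent Data Monitoring Committee (DMC) will recommend whether to continue, modify or terminate". Its members are two liver surgeons from outside the sponsor's hospital. Apart from the contents list, the DMC appears nowhere else, and no periodic review, toxicity trigger or charter is cited.
- **The main drug harm.** Section 5.1.4.7: "The most important serious adverse drug reaction is biliary toxicity". Section 5.1.4.11 gives a reference rate: "The incidence of biliary sclerosis due to HAIP chemotherapy in a retrospective analysis of 293 patients was 5.5"%. It then says: "All patients were managed successfully with biliary stenting and/or dilatation".
- **Other safeguards.** Section 5.1.4.8 says "complete blood counts and liver function tests are monitored every 2 weeks during HAIP chemotherapy". Its Table 2 reduces or holds the dose, and a bilirubin above 3.0 mg/dL ends floxuridine permanently. SAEs reach the sponsor within 24 hours and feed a risk/benefit evaluation (6.3.1). Reactions unexpected in nature or severity are reported as SUSARs (6.1.5, 6.3.2). There is a yearly report to the Competent Authority (6.3.3), monitoring of HAI-arm event reporting (7.3) and ethics committee notice of serious, unexpected events (11.1). The PI or sponsor may stop the trial (5.8.2).

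**The concern.** The written trigger responds to death from any cause. In this population most deaths will plausibly come from the cancer, so a DMC meeting prompted by one says little about drug safety. The harm the protocol itself ranks first is usually survivable and does not convene the committee at all.

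Section 1.7 says HAI is not offered in Norway and that the drug has no European marketing authorisation, so this is a new programme at one centre. Whether its biliary complication rate is acceptable is a question an independent committee is well placed to judge. The gap is widest if HAI prolongs survival while injuring bile ducts: deaths come late, and patients who do well without resection may receive more cycles, which section 5.1.4.11 lists as a risk factor for sclerosis. If HAI fails, deaths convene the DMC early anyway.

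**Working it through.** Section 6.5 states no figure to reproduce. The checks are how often and when the death trigger fires, and what a biliary count would add.

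**Inputs from the protocol.** 18 patients randomised to HAI and a 75% two-year survival target, against 30% for standard care (8.1). Three-year recruitment (3). Sclerosis 5.5% of 293, about 16 cases (5.1.4.11). Treatment duration 24 weeks (synopsis). "A laparotomy is performed within 2 weeks from randomization" (5.5). "All patients start HAIP chemotherapy 4 to 8 weeks after surgery" (5.1.4.6).

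**Assumptions.** HAI entries evenly spaced at months 1, 3, …, 35. Constant hazard, with follow-up counted to 24 months each. Deaths independent of sclerosis. Sclerosis rates above 5.5% and the 50% survival scenario are illustrative.

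**1. Does the death trigger fire?** With n = 18 and 75% survival:
- P(at least one death) = 1 − 0.75^18 = 0.994. At 30% survival it exceeds 0.9999.
- Expected deaths = 18 × 0.25 = 4.5.
- P(two or more) = 1 − 0.75^18 − 18 × 0.25 × 0.75^17 = 1 − 0.006 − 0.034 = 0.96.

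**2. When?** P(no HAI death by month t) = S^(M/24), where M is the accumulated patient-months.

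| Month | M | S = 0.75 | S = 0.50 | S = 0.30 |
|---|---|---|---|---|
| 12 | 36 | 0.65 | 0.35 | 0.16 |
| 18 | 81 | 0.38 | 0.10 | 0.02 |
| 24 | 144 | 0.18 | 0.02 | <0.01 |
| 36 | 288 | 0.03 | <0.01 | <0.01 |

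**3. How would a biliary count behave?** Candidate rule: 2 or more of the first 6 treated, or 3 or more of all N treated. The early part is binomial with n = 6. The combined probability is P(X6 ≥ 2) + P(X6 = 0)·P(Y ≥ 3) + P(X6 = 1)·P(Y ≥ 2), where X6 counts cases in the first 6 and Y counts cases in the other N − 6. N = 16 allows for patients who never start: in the cited pump series "HAIP chemotherapy with floxuridine was impossible or discontinued in only 9% of patients", and 18 × 0.91 ≈ 16.

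| True sclerosis rate | 2+ of first 6 | Either, N = 18 | Either, N = 16 |
|---|---|---|---|
| 5.5% | 0.04 | 0.09 | 0.08 |
| 10% | 0.11 | 0.29 | 0.25 |
| 20% | 0.34 | 0.75 | 0.67 |
| 30% | 0.58 | 0.94 | 0.91 |

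The Clopper-Pearson 95% interval for 16/293 is 3.2% to 8.7%. At those limits the combined rule with N = 18 fires with probability 0.03 and 0.23.

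**4. What does the count add by month 12?** Gain = P(no death yet) × P(early count met). Six patients have entered by then, but not all have had meaningful exposure. Up to 2 weeks to laparotomy plus 4 to 8 weeks to first FUDR gives a lag of about 1 to 2.5 months. I spread each patient's risk evenly over 24 weeks (5.52 months) from first FUDR. The fraction of risk accrued by month 12, in entry order, is:
- lag 1 month: 1, 1, 1, 0.72, 0.36, 0
- lag 2.5 months: 1, 1, 0.82, 0.45, 0.09, 0

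Example at a 20% rate and lag 1: the individual risks are 0.20, 0.20, 0.20, 0.145, 0.072 and 0. P(none) = 0.406 and P(exactly one) = 0.405, so P(two or more) = 0.189. At 75% survival the gain is 0.650 × 0.189 = 0.12.

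| Sclerosis rate | P(2+ by month 12), lag 2.5 to lag 1 | Gain, S = 0.75 | Gain, S = 0.50 | Gain, S = 0.30 |
|---|---|---|---|---|
| 5.5% | 0.012–0.018 | 0.01 | <0.01 | <0.01 |
| 10% | 0.038–0.056 | 0.02–0.04 | 0.01–0.02 | 0.01 |
| 20% | 0.133–0.189 | 0.09–0.12 | 0.05–0.07 | 0.02–0.03 |
| 30% | 0.264–0.358 | 0.17–0.23 | 0.09–0.13 | 0.04–0.06 |

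**The case against.** The strongest reply is that this is a preference about safety governance in a small, open-label, single-centre phase II trial, and that biliary toxicity is already handled. Much of that stands:
- A reader might infer that non-fatal biliary toxicity goes unwatched. It does not. Section 5.1.4.8 is a firm drug-specific rule for each patient, serious events reach the sponsor within a day, and a biliary reaction of unexpected severity is a SUSAR. What none of these routes does is put an excess number of expected-severity events before the independent committee.
- A reader might infer that the DMC will rarely meet or may look only at deaths. Neither follows. At 75% survival 4.5 HAI deaths are expected, and section 6.5 does not restrict what the committee sees. By month 24 it has probably been convened.
- A reader might infer that a single death stops the trial. It prompts a recommendation only.
- A reader might put all six early patients at full risk by month 12. That gives gains of 0.650 × 0.345 = 0.22 at a 20% rate and 0.650 × 0.580 = 0.38 at 30%. The protocol's own timetable does not support this: the sixth patient starts FUDR at about month 12 to 13, and risk rises with cycles. The realistic gains are roughly half.

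A count of sclerosis cases also needs an attribution rule. These patients have six or more liver metastases, and section 5.1.4.10 asks for a CT before drainage because tumour can itself obstruct the ducts. The fix has to include this.

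**Conclusion.** The point holds in a limited form. The only written DMC trigger is a death in the HAI arm. It is close to certain to fire, probably more than once, but at times unrelated to the drug's main known toxicity. The uncovered case is an excess frequency of expected, non-fatal biliary events before the first HAI death.

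The size is modest. At 75% survival there is a 0.65 chance that the DMC has not been convened by month 12, falling to 0.03 by month 36. The added chance of review by month 12 is about 0.01 at the cited 5.5% rate and reaches 0.17–0.23 only at an assumed 30%; it is smaller if survival is worse.

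These figures rest on even accrual, constant hazard, independence of death and sclerosis, and risk spread over 24 weeks of FUDR. Section 5.1.4.9 allows treatment until progression, and slower accrual of risk would lower the gains. Section 5.1.4.6 also gives a two-week minimum before starting, and a shorter lag would raise them somewhat. No analysis, sample size or primary conclusion is affected.

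**What to change.** Keep the death trigger in section 6.5 and add:

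*The DMC will also review the trial if biliary sclerosis requiring stenting, dilatation or drainage, with tumour obstruction excluded on CT, occurs in 2 or more of the first 6, or in 3 or more of all, patients who have received FUDR. At every review the DMC will also see permanent floxuridine discontinuations for biliary toxicity.*

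The denominator is patients who received FUDR, to match the cited series, and the last sentence brings in biliary toxicity that ends treatment without an intervention.

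**Cost.** A short protocol amendment, using the same two-member committee and adverse event data already recorded in the CRF. Someone must apply the CT exclusion case by case. The chance of an unneeded review is about 9% at the 5.5% rate (3% to 23% over its confidence interval), and could be slightly higher because drainage widens the event beyond the series' stenting and dilatation. The early count is a weak detector: at a true rate of 20% it fires in only about one third of cases, so it supplements the existing safeguards and does not replace them.

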7 DATA MANAGEMENT AND MONITORING

7.1 Case Report Forms

The Clinical Data Management System (CDMS) used for the eCRF in this study is EpiData. The setup of the study specific eCRF in the CDMS will be performed by Clinical Project assistant, OUS.

The designated investigator staff will enter the data required by the protocol into the eCase report forms (eCRF). The Investigator is responsible for assuring that data entered into the eCRF is complete, accurate, and that entry is performed in a timely manner. The signature of the investigator will attest the accuracy of the data on each eCRF. If any assessments are omitted, the reason for such omissions will be noted on the eCRFs. Corrections, with the reason for the corrections will also be recorded.

After database lock, the investigator will receive a digital copy of the subject data for archiving at the investigational site.

7.2 Source Data

Source data are all information in original records and certified copies of original records of clinical findings, observations, or other activities in a clinical trial necessary for the reconstruction and evaluation of the trial. Source data are contained in source documents (original records or certified copies).

The medical records for each patient should contain information which is important for the patient's safety and continued care, and to fulfill the requirement that critical study data should be verifiable.

To achieve this, the medical records of each patient should clearly describe at least:

- That the patient is participating in the study, e.g. by including the enrollment number and the study code or other study identification;
- Date when Informed Consent was obtained from the patient and statement that patient received a copy of the signed and dated Informed Consent;
- Results of all assessments confirming a patient's eligibility for the study;
- Diseases (past and current; both the disease studied and others, as relevant);
- Surgical history, as relevant;
- Treatments withdrawn/withheld due to participation in the study;
- Results of assessments performed during the study;
- WHO performance status assessments conducted as part of the study, if applicable;
- Treatments given, changes in treatments during the study and the time points for the changes;
- Visits to the clinic / telephone contacts during the study, including those for study purposes only;
- Non-Serious Adverse Events and Serious Adverse Events (if any) including causality assessments;
- Date of, and reason for, discontinuation from study treatment;
- Date of, and reason for, withdrawal from study;
- Date of death and cause of death, if available;
- Additional information according to local regulations and practice.

A source data list will be agreed upon for each site specifying the source at a module or a variable level.

